IRB Study Number: TBD

Title: Patient Well-Being Research Project 01-23-17 to IRB

Protocol Title

Title: **Patient Well-Being Research Project**

Objectives

Well-being is a positive state affairs in six domains of life: interpersonal, community, occupational, physical, psychological, and economic (I COPPE). The purpose of the study is to evaluate the effectiveness, feasibility, and acceptability of an online intervention designed to promote skills and self-efficacy in the I COPPE domains of life.

Overview

The study design is a prospective, double-blind, longitudinal randomized controlled trial (RCT). The control group will be wait-listed. Well-being and self-efficacy measures will be administered at baseline (T1), 30 days-post baseline (T2) and 60 days -post baseline (T3). Approximately 6,000 University of Miami Health System (UHealth) patients who visit the UM Lennar Foundation Medical Center may have the opportunity to be invited to participate in the study. A maximum of 500 patients will be enrolled. Recruitment will take place on-site through IRB approved study flyers at the UM Lennar Foundation Medical Center. Eligibility verification, data collection, randomization, intervention group activities, and incentive distribution will take place entirely online. A secure website will be the sole location where all research activities will take place. Participants will only be able to access the site using unique user names and passwords. After consenting, participants in the intervention group will participate in online activities within 30 calendar days. Participants in the wait-list control group will be given access to the intervention after all study participants have completed the three survey battery administrations. The study team has full support at the highest administrative levels of the University of Miami.

IRB Study Number: TBD

Title: Patient Well-Being Research Project 01-23-17 to IRB

Intervention condition: Through the online program named Fun For Wellness (FFW), participants will: 1) watch original videos with vignettes performed by professional actors; 2) read and/or watch mini-lectures that teach skills for behavior change; 3) engage in self-reflection exercises, 4) play original interactive games related to vignettes and mini-lectures; 5) interact with other FFW users via chat room functions and; 6) watch funny narrated video clips about well-being.

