As previously mentioned, the study design is a prospective, double-blind, longitudinal randomized controlled trial (RCT). Well-being and self-efficacy measures will be administered at baseline (T1), 30 days-post baseline (T2) and 60 days -post baseline (T3). Approximately 1,000 University of Miami Health System (UHealth) patients from the UM Lennar Medical Center will be invited to participate in the study. A maximum of 500 patients will be enrolled. Recruitment will take place on-site through distribution of IRB approved study flyers at the UM Lennar Center. Eligibility verification, data collection, randomization, intervention/control group activities, and incentive distribution will take place entirely online. A secure website will be the sole location where all research activities will take place.

Data Collection Plan

At each individually scheduled data collection point, participants will have a 7-day window to return to the website and provide their survey data (see Battery below) in order to receive an incentive. If they do not return within the 7-day timeframe to provide survey data, this will be considered missing data. All participants must complete/participate in each survey battery set to be credited money in the study’s Amazon electronic gift card account. Completion of each

IRB Study Number: TBD

Title: Patient Well-Being Research Project 01-23-17 to IRB

survey will be marked by a final SUBMIT button for the participant to click on when they are ready to submit each survey as completed. During each data collection time (i.e., T1, T2, T3), each participant will be able to see how far he/she has progressed toward completion of a survey battery set in order to be eligible for the assigned incentive value for that particular data collection time (i.e. \$5, \$10, \$15). This will be accomplished by providing each participant with a progress bar that will be visually represented on the participant's data collection page. The participant will be able to view how many surveys and items he/she has to complete to achieve completion.

Remuneration Plan

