30 days has passed from the day each participant was randomly assigned to their group (intervention or control), she/he will be sent an e-mail reminding her/him to return to the website to complete some more surveys and receive an additional \$10 electronic gift card credit. For intervention group participants, those participants who completed at least 50% of each of the 15 modules will also be credited \$15 of Amazon electronic gift cards in their account. After an additional 30 days, each participant will be e-mailed again to return to the website for the last time to complete the final set of surveys and receive the final additional \$15 electronic gift card credit. After each participant has completed the final surveys, she/he will be e-mailed codes to redeem the total amount of Amazon electronic gift cards he/she has been credited throughout her/his Patient Well-Being Research Project experience. In total, each intervention participant will have the opportunity to obtain \$45 worth of Amazon electronic gift cards. Control group participants will have the opportunity to obtain a total of \$30 in Amazon electronic gift cards.

The following italicized text is the message participants will be presented immediately after they complete and submit the 3rd battery set of surveys.

“Thank you for completing this set of surveys. Around [Date] we will send you an email with instructions on how to redeem your Amazon electronic gift codes.”

Participant Recruitment Plan

The study aims to consent (i.e. enroll), assess, and randomly assign no more than 500 participants in a rolling fashion in real-time within an online environment. A timeframe of 24-calendar days will be considered the “recruitment window” to achieve this enrollment aim.

During the recruitment window the following research activities will take place simultaneously across multiple participants: 1) participant recruitment; 2) Patient Well-Being Research Project personal account creation; 3) e-mail validation procedure; 4) screening; 5) consenting; 6) data

IRB Study Number: TBD

Title: Patient Well-Being Research Project 01-23-17 to IRB

collection of baseline (T1) survey battery set; 7) participant incentive #1 credit deposit; 8) participant randomization and condition group assignment; 9) participant-intervention group online program access

[figure not shown]
Recruitment Window Procedures

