The first participant who submits their T1 battery will be assigned control or intervention based on a digital coin flip. For each additional participant who submits their T1 battery, if we need another person to fulfill the intervention (2:1) ratio, that person will be assigned to the intervention condition. The same with control, if more control participants need to be assigned to that condition, then the participant will be added to the control group. If we already have an exact 2:1 ratio, the participant will be assigned to one of the two conditions based on a digital coin flip.

9) Participant condition group access. As soon as participants complete the T1 battery set of surveys and are randomized by the computer, they will be sent a welcome e-mail. Here is the e-mail subject line: *Welcome to the Patient Well-Being Research Project*.

Intervention participants will have immediate access to the Fun For Wellness and control participants will be wait-listed. Participants in the intervention group may access the Patient Well-Being Research Project site during all hours of the 30-day access window. Control group participants will be informed they have been randomly assigned to the wait-list condition and will be given eventual 30 days of access to the online well-being program at the end of the 60-day study.

After 30 days, participants in the intervention group will no longer have access to the online program at the Patient Well-Being Research Project site. Participants from both condition groups may still log in to see how much credit they have in their account to redeem Amazon electronic gift card codes. Participants in both groups will be sent reminder e-mails to complete the survey set for the second time (T2: 30-days post baseline). After 30 more days have passed (T3: 60-days post baseline), participants will receive reminder e-mails to complete the survey set for the third time.

IRB Study Number: TBD

Title: Patient Well-Being Research Project 01-23-17 to IRB

10) Participant e-mail reminder plan. Two types of e-mail reminders will be automatically sent to participants during the 60-day study period. The first type of e-mail will encourage continued participation in the online program. The second type of email will encourage completion of the surveys.

a) Email to encourage continued participation:

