We will send one participation e-mail during the intervention participant's 30-day access period. One e-mail will be sent to each participant on day 4 of their 30-day access period.

Here is the day 4 participation encouragement e-mail subject line: ***Patient Well-Being Research Project- 26 more days to keep visiting us during your access time 😊***

b) Email to encourage survey completion:

We will send four of these survey completion emails to participants in both condition groups. For each data collection time (T2; T3), we will send two survey battery reminder e-mails. At T2, immediately after the intervention group participant's 30-day access period, and after 30 days have passed since the T1 baseline for the wait-list control participant (i.e., day 31), we will send one survey battery reminder e-mail. Four days later, we will send another survey battery reminder e-mail to those participants who have still not completed T2 data collection.

Here is the T2 (day 31) initial survey battery reminder e-mail subject line: ***Patient Well-Being Research Project: Reminder 7 days to complete Survey Set #2.***

IRB Study Number: TBD

Title: Patient Well-Being Research Project 01-23-17 to IRB

Here is the T2 (day 34/day 4 of 7-day window) initial survey battery reminder e-mail subject line: ***Patient Well-Being Research Project: Reminder 3 days to complete Survey Set #2.***

On the first day of T3, which corresponds to 60-days post baseline, we will send one survey battery reminder e-mail that the 7-day window is open for participants to complete the third survey battery set. Four days later, we will send another survey battery reminder e-mail to those participants who have still not completed T3 data collection.

Here is the T3 (60-day post baseline) initial survey battery reminder e-mail subject line: ***Patient Well-Being Research Project: Reminder 7 days to complete Survey Set #3.***

Here is the T3 (60-day post baseline) (day 64/day 4 of 7-day window) initial survey battery reminder e-mail subject line: ***Patient Well-Being Research Project: Reminder 3 days to complete Survey Set #3.***

Battery Set of Surveys Content

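### The two statements of when wait-list controls get program access differ, and one of them, applied as day 60, would open the program while a control's T3 survey is still pending

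*Combined protocol and SAP*

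**What the plan says.** Under Recruitment Window Procedures, item 9 (Participant condition group access), controls are told of their wait-list assignment and "will be given eventual 30 days of access to the online well-being program at the end of the 60-day study". Nothing there makes access depend on the control's own T3 survey or on other participants.

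The Overview gives a different trigger: controls are to be "given access to the intervention after all study participants have completed the three survey battery administrations".

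The T3 timing is in item 10 (Participant e-mail reminder plan): "On the first day of T3, which corresponds to 60-days post baseline, we will send one survey battery reminder e-mail". A second reminder follows four days later to those who have not answered, and its label reads "day 64/day 4 of 7-day window) initial survey battery reminder e-mail subject line". The Data Collection Plan sets the length of each survey period: "participants will have a 7-day window to return to the website and provide their survey data". It treats non-return within that time as missing data.

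Enrolment is rolling. The Participant Recruitment Plan states: "A timeframe of 24-calendar days will be considered the “recruitment window” to achieve this enrollment aim". Each participant therefore has a separate 60-day clock. The descriptions of the wait-list condition near the start of the protocol and under Group Conditions give no access date, so they do not settle the matter.

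**The concern.** One trigger depends on elapsed time and the other on everyone's surveys. With rolling enrolment these can fall on different dates for most controls. Access is controlled by software, so one condition has to be coded, and the text does not say which.

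If the elapsed-time trigger is coded as day 60, controls get the program just as T3 opens. The T3 e-mail calls them back to the same site that hosts the program, and the I COPPE items ask, among other things, where the respondent stands now. A control who uses the program first and answers afterwards is no longer an unexposed comparator at that visit.

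T3 is the last of three points in the trajectories compared under H1 and H2 and used for mediation under H3, so it carries much of the information on the slope. If the program helps, early use by controls would pull the arms together at T3. The Data Analysis Plan has no provision for control exposure.

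**Working it through.** The plan has no figure of its own to reproduce here, so the check is day arithmetic.

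**Inputs**
- Enrolment (baseline) day *r* = 1 to 24, from the Participant Recruitment Plan.
- T3 window of 7 days, from the Data Collection Plan.
- T3 opening day *s*. Item 10 supports two counts. The first day of T3 is placed at 60 days after baseline, giving *s* = 60. Day 64 is labelled day 4 of the window, and 64 − 3 = 61, giving *s* = 61. Both are carried through.
- Calendar day = *r* + days since baseline. The T3 window runs from *r* + *s* to *r* + *s* + 6, that is, days 60–66 or 61–67 on the participant's own clock.

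**Reading 1: access at the control's own day 60.** Access opens on calendar day *r* + 60. All 7 window days are at or after that point under both counts. Access can precede the T3 answer by up to 66 − 60 = 6 days, or 67 − 60 = 7 days. This holds for every enrolment day.

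**Reading 2: access at the last enrollee's day 60.** This is calendar day 24 + 60 = 84. A control's window is still open that day if *r* + 66 ≥ 84, so *r* ≥ 18, or if *r* + 67 ≥ 84, so *r* ≥ 17. Controls enrolled on days 18–24 (or 17–24) would still overlap. This reading reduces the problem without removing it.

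**Reading 3: access after the control's own T3 window has closed.** There is no overlap. For *r* = 1 the window closes on calendar day 1 + 66 = 67 (or 68).

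**Reading 4: the Overview trigger, with a closed window counted as finished.** The last window closes on calendar day 24 + 66 = 90 (or 91), and access follows. There is no overlap for anyone. For *r* = 1 this is 90 − 61 = 29 days (or 30) after that control's own 60-day mark. For *r* = 24 it is 90 − 84 = 6 days (or 7).

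Readings 3 and 4 both protect T3 but are not the same rule: for a control enrolled on day 1 the windows that govern access close 90 − 67 = 23 days apart (91 − 68 = 23 under the other count).

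**What cannot be computed.** The size of any dilution would need the share of controls who enter the program before answering T3, the program's effect, and how quickly that effect appears. The documents give none of these.

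**The case against.** The strongest reply is that the 60-day phrase is loose shorthand that includes T3. Item 9 is followed directly by a statement that all e-mail reminders go out within the 60-day period, and those include the day-64 T3 reminder. The unsubscribe instructions use the end of the 60-day study for the time when all gift codes are owed, and the Remuneration Plan sends codes only after the final surveys. Item 9 also promises access eventually and names no day. If the study is taken to end when survey administration ends for everyone, item 9 is a short form of the Overview and the two agree.

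This stands as a possible reading, and it is why the overlap is stated as something that could happen. It does not settle the text. After one's own T3 is still different from after everyone's T3, and nothing in item 9 blocks access before the T3 survey is submitted.

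Three stronger conclusions are tempting and are not supported:
- A reader might infer that the two statements are irreconcilable. The shorthand reading above shows that they can be brought together.
- A reader might infer that the Overview trigger could never be met once one survey is missed. The Data Collection Plan closes each battery after 7 days and records non-return as missing, so having finished can fairly mean that the windows have closed. The wording should say so, but it is not unworkable.
- A reader might infer that T3 answers from exposed controls should be left out of the main comparison. That would condition the contrast, in one arm only, on behaviour after randomisation and could introduce selection bias.

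**Conclusion.** The concern holds as a conditional one. The protocol states the wait-list access time in two ways that do not match as written, and one of them, applied as day 60, lets every control into the program during that control's T3 window, by up to 6 or 7 days before the answer. Taking the last enrollee's day 60 instead still leaves controls enrolled in roughly the final week of recruitment exposed.

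The probable effect, if the program works and some controls use it early, is dilution of the T3 contrast and the slope difference. This rests on two assumptions: that item 9 is implemented as elapsed days, and that some controls use the program before answering. A reader might take the contamination as certain or try to put a percentage on it. The documents support neither. It is worth resolving before launch because prevention is cheap and exposed T3 answers cannot be recovered.

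**What to change.** Reconcile the Overview and item 9 into one access rule, stated identically in both places and in the message shown to controls. The choice of date belongs to the investigators. For the analysis, the rule needs two properties:
1. No control has program access while that control's T3 window is open.
2. A closed 7-day window counts as finished, so that missed surveys do not block access.

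State also whether T3 opens on day 60 or day 61, since the rule depends on it.

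In the Data Analysis Plan, keep all control T3 values in the main as-randomised analysis. If any control is found to have used the program before T3, examine this in a sensitivity analysis only. First confirm that the site records dated access for controls. The Participation measures section lists visit counts and time per module, but no passage says that dated log-ins are kept.

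The cost is protocol wording, one software condition and a sentence on the sensitivity analysis. Some controls may wait longer: 6 to 7 days past their own day 60 if access follows the close of their own window, or up to 29 to 30 days for the earliest enrollees if it follows the close of everyone's.

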Throughout participation in the Patient Well-Being Research Project, each participant will be credited in the study to receive Amazon electronic gift cards as a thank you for completing/submitting each set of surveys (i.e. battery), for each of the three data collection times. They will need to submit the final answers of each survey before moving onto the next survey of the battery. The computer program offers the participant an opportunity to leave items blank or click on an item response if they wish by presenting a one-time pop-up reminder that states, "Are you sure you want to leave this item blank?" Therefore, a participant may skip items by choice during a particular survey answering experience, but in order to get the Amazon gift credit for that data collection time, the participant must submit each survey to complete participation in the full battery set for each data collection time. Intervention group participants will also have the opportunity to earn Amazon gift cards in addition to those earned by survey completion, based on their participation in the online intervention.

At the very start of participation by completing the first set of surveys, each participant will be credited \$5 toward an Amazon electronic gift card. For participants in both groups, when

IRB Study Number: TBD

Title: Patient Well-Being Research Project 01-23-17 to IRB

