Title: Patient Well-Being Research Project 01-23-17 to IRB

represented visually on the user's page as they complete each assessment to show their level of battery completion. Below is the T1 battery set of assessments that all consented participants will be administered prior to being randomized to a condition group.

1. FFW Demographics Questionnaire (9 items)
2. Self-Efficacy to Comply Measure (1 item)
3. I COPPE Scale- 30-day version (21 items)
4. SEWB Scale- 30-day version (21 items)
5. I COPPE Actions Scale- Revised (19 items, including 1 attention filter item)
6. Chronic Conditions Checklist (20 items)
7. SF-36 v2 (36 items)

On day 14 of the recruitment window, a baseline (T1) data collection battery set reminder e-mail will be sent to all consented participants who have not completed T1 data collection letting them know they have 10 more days to complete the T1 battery set of surveys. Here is the e-mail subject line: ***Patient Well-Being Research Project: Reminder to complete Survey Set #1.***

7) Participant incentive #1 credit deposit. After each participant submits the final survey, a visual and sound action will show the \$5 Amazon electronic gift card credit into the participants' Patient Well-Being Research Project bank account.

8) Participant randomization and condition group assignment. Participants who have completed the full T1 battery will be randomly assigned in real time to either the intervention condition or the wait-list control condition. Randomization and assignment will be done solely by the computer program so researchers will be blind to participant randomization and group assignment. The computer program will use a 2:1 randomization algorithm so that there are twice as many intervention participants as control participants. Participants will be randomly assigned based on their sequential order in the assignment line up which will be established at the exact time of each participant's submission of the battery of the first set of surveys (i.e. T1).

IRB Study Number: TBD

Title: Patient Well-Being Research Project 01-23-17 to IRB

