Question contexts effects (i.e., where questions are located in a survey, what questions precede an item) have been found to influence respondent survey choices on measures of subjective well-being (Schwarz & Strack, 1999; OECD, 2013) and self-rated health (Lee, McClain, Webster, & Han, 2016). Therefore, to avoid artificial attenuation or inflation in their relationship, the subjective well-being measure (I COPPE Scale) will be presented well before the chronic conditions checklist, and health-related quality of life measures.

IRB Study Number: TBD

Title: Patient Well-Being Research Project 01-23-17 to IRB

The entire battery set of surveys, consisting of 127 items in total, and the order of how the surveys will be presented to respondents is as follows:

1. FFW Demographics Questionnaire (9 items)
2. Baseline_Self-Efficacy to Comply Measure (1 item)
3. I COPPE Scale- 30-day version (21 items)
4. SEWB Scale- 30-day version (21 items)
5. I COPPE Actions Scale- Revised (19 items, including 1 attention filter item)
6. Chronic Conditions Checklist (20 items)
7. SF-36 v2 (36 items)
8. FFW Experience Survey (15 items) [intervention group only T2]

Battery Administration Schedule

T1 (baseline): both condition groups

- 1) FFW Demographics Questionnaire
-9 items
- 2) Self-efficacy to Comply Measure
-1 item
- 3) I COPPE Scale 30-day version
-21 items
- 4) Self-Efficacy in Well-Being Domains Scale (SEWB) 30-day version
- 21 items
- 5) I COPPE Actions Scale
- 18 items + item #19 attention filter
- 6) Chronic Conditions Checklist
-20 items
- 7) SF36 v2
-36 items

T2 (30-days post baseline): both condition groups

- 1) I COPPE Scale 30-day version
-21 items
- 2) Self-Efficacy in Well-Being Domains Scale (SEWB) 30-day version
- 21 items

IRB Study Number: TBD

Title: Patient Well-Being Research Project 01-23-17 to IRB

- 3) I COPPE Actions Scale
- 18 items + item #19 attention filter
- 4) SF36 v2
-36 items

T2 (30-days post baseline): intervention only

- 5) FFW Experience Survey
-15 items

T3 (60-days post baseline): both condition groups

- 1) I COPPE Scale 30-day version
-21 items
- 2) Self-Efficacy in Well-Being Domains Scale (SEWB) 30-day version
- 21 items
- 3) I COPPE Actions Scale
- 18 items + item #19 attention filter
- 4) SF36 v2
-36 items

Description of Measures

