4) I COPPE Actions Scale. The I COPPE Actions Scale is a self-report measure created for this study. The measure consists of 18 items which tap behavioral outcomes in the six I COPPE constructs. The creation of this instrument is based on the literature reviewed in the section above named “I COPPE Domains”. Each construct is comprised of three items measuring the frequency of engagement in behaviors aligned with the six constructs. Each item is rated on a scale of 0-4 where the lowest value means “very rarely or never” and the highest value means “very often or always”. The six constructs and their respective definitions follow:

- a) **INTERPERSONAL:** Engaging in activities that promote satisfaction in important relationships in life
- b) **COMMUNITY:** Engaging in activities that promote satisfaction as well as involvement and sense of belonging in one’s community

IRB Study Number: TBD

Title: Patient Well-Being Research Project 01-23-17 to IRB

- c) OCCUPATIONAL: Engaging in activities that promote satisfaction with main occupation such as work, volunteering, or caring after relatives
- d) PHYSICAL: Engaging in activities that promote physical health and well-being
- e) PSYCHOLOGICAL: Engaging in activities that promote emotional and psychological well-being
- f) ECONOMIC: Engaging in activities that promote economic well-being

***Attention Filter item #19 of the I COPPE Actions Scale.** Given the common problem of random responding on online surveys (i.e. clicking through), the attention filter item, “*Please select number 3*”, has been included at the end of the I COPPE Actions Scale. This is to ensure respondents are providing valid responses. If respondents are paying attention they are expected to select number 3. If a respondent clicks any other answer, the respondent’s data will be considered invalid for that battery time.

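### Submitted T2/T3 batteries are treated as invalid on one attention item answered after randomization, with no by-arm failure count and no analysis that keeps them

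*Combined protocol and SAP*

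**What the plan says.** - **The rule.** Description of Measures, 4) I COPPE Actions Scale, attention filter item #19: if the respondent clicks anything but 3, the respondent's "data will be considered invalid for that battery time". The wording covers the whole battery, not only the Actions Scale. The stated aim is to catch random clicking.
- **When it applies.** The Battery Administration Schedule lists the item at T1, T2 and T3; the last of these is headed "T3 (60-days post baseline): both condition groups". At T2 and T3 it comes after the I COPPE Scale and SEWB and before the SF-36v2.
- **Randomization comes first.** Study Procedures, step 8: "Participants who have completed the full T1 battery will be randomly assigned in real time". The T2 and T3 items are therefore answered after allocation.
- **Arm is known.** Step 9: "Control group participants will be informed they have been randomly assigned to the wait-list condition".
- **Blanks are allowed.** Remuneration Plan: "a participant may skip items by choice during a particular survey answering experience". The filter rule speaks of clicking another answer and does not classify a blank item #19.
- **Missing data.** Data Collection Plan: "If they do not return within the 7-day timeframe to provide survey data, this will be considered missing data". This does not mention attention failures.
- **Analysis.** Hypotheses and Methods (H1 to H3) describes growth and mediation models. It names no analysis set, missing-data method or sensitivity analysis, and does not mention item #19.

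**The concern.** Randomization makes the two groups comparable as allocated. A rule that removes follow-up outcomes because of something participants do afterwards can undo this. The filtered comparison stays unbiased if failers do not differ from passers, or if failure rates and failer-passer gaps are the same in both arms. Neither condition can be assumed. The arms have had different experiences by T2, and participants know which one they are in, whatever the double-blind label says.

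One click affects the outcomes of H1, H2 and H3 together. If failure did differ by arm, the estimate would shift in an unknown direction and no planned output would show it. Without a stated plan, the choice between filtered and unfiltered results could also be made after both have been seen.

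**Working it through.** The plan states no failure rate, effect size, power or attrition figure, so there is nothing of its own to reproduce. What follows is illustration under stated assumptions.

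**Inputs from the documents.** At most 500 participants, 2:1, so about 333 intervention and 167 control; three waves; item #19 at T2 and T3 in both arms.

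**Assumed.** Failure of 5 to 15% per battery; failers lower than passers by d = 0.25 to 1 SD; between-wave correlation 0.5 to 0.7; two-sided 5% test, 80% power.

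**1. Is there a structural reason for a large arm difference?** Items answered before #19 at T2 and T3: 21 + 21 + 18 = 60 in both arms. The 15 extra intervention items at T2 come later, and each survey is locked in first ("They will need to submit the final answers of each survey before moving onto the next survey of the battery"). The T3 batteries are identical. So the layout gives no such reason.

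**2. Single-wave bias from voiding failers.** Voiding a share p of an arm whose failers lie d below its passers raises that arm's mean by p × d, so bias = p1·d1 − p0·d0.
- Equal rates and gaps: 0.
- 10% v 5%, d = 0.25: 0.05 × 0.25 = 0.0125 SD.
- 15% v 5%, d = 1: 0.10 × 1 = 0.10 SD.

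The sign reverses if control fails more.

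**3. Three-wave linear growth model.** Expected generalized least squares estimate, arm-specific intercepts and slopes, compound symmetry, T1 kept, T2/T3 voided for failers; bias in the 60-day arm difference (2 × the slope difference):

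| Rates and gap | Gap only at voided waves | Gap a stable trait, same people fail |
|---|---|---|
| 10% v 5%, 0.25 SD | 0.013 SD | 0.004 to 0.006 SD |
| 15% v 5%, 1 SD | 0.10 SD | 0.030 to 0.051 SD |

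A stable gap is partly corrected because T1 already shows it.

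**4. Scale.** Detectable difference at a single wave: 2.80 × √(1/333 + 1/167) = 0.266 SD. In the growth model it is 0.266 SD at correlation 0.5 and 0.206 SD at 0.7.

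**5. Precision.** Voiding T2/T3 at 5% and 15% raises the slope standard error by about 2% and 6 to 7%.

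**6. What keeping all batteries does.** Suppose failed batteries carry no signal and the true effect is 0.30 SD (assumed). The estimate is (1 − p1) × 0.30 + (p1 − p0) × r, where r is the mean of no-signal answers relative to control passers.
- Equal 5%: 0.95 × 0.30 = 0.285 SD.
- Equal 15%: 0.85 × 0.30 = 0.255 SD.
- 10% intervention v 5% control, r from 0 to −1: 0.27 down to 0.27 − 0.05 = 0.22 SD.
- 5% intervention v 10% control, r from 0 to −1: 0.285 up to 0.285 + 0.05 = 0.335 SD.

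**The case against.** The rule is fixed in advance, objective, the same in both arms and meant to protect data validity. If failure rates and gaps are equal, the filter is unbiased, while keeping every battery dilutes a 0.30 SD effect by 0.015 to 0.045 SD when failed batteries are noise. At 10% v 5% failure with the intervention arm failing more, keeping everything errs by 0.03 to 0.08 SD, against 0.0125 to 0.05 SD for the filter at gaps of 0.25 to 1 SD. This stands. A reader might infer that the unfiltered analysis must be primary; the documents and these figures do not settle that, and either can be the better estimate.

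The bias range is wholly assumed. This also stands: the top value needs a threefold difference in failure and a 1 SD gap. A reader might infer that the result is likely to be materially biased, or that the longer intervention battery at T2 drives failures. Neither is supported, because the items before #19 are the same in both arms.

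The text says invalid, not deleted. True, but it gives no other use for invalid data. Likelihood estimation could retain a person's other waves, but not the voided outcomes, and no estimator is stated. The Data Collection Plan defines non-return as missing; it does not say that nothing else is.

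The rule also covers T1. That item is answered before allocation, so failure there cannot depend on arm and costs only precision (about 2 to 6% in the slope standard error). It is not part of this point.

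**Conclusion.** The point holds as a modest, inexpensive improvement. On its natural reading, a stated rule removes submitted T2/T3 outcomes of randomized participants because of behaviour after randomization, and nothing planned would reveal an imbalance. Bias is zero at equal failure rates and gaps. Under the assumed ranges it is about 0.004 to 0.10 SD, probably near the low end, against a detectable difference of about 0.21 to 0.27 SD. Failure rates, gaps and correlations are assumptions; none is in the documents. The conclusion that does not depend on them is that the filtered analysis alone cannot show whether the filter mattered.

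**What to change.** For T2 and T3, add to the Data Analysis Plan:
1. An as-randomized analysis that keeps every submitted battery, reported beside the analysis that excludes batteries failing item #19.
2. A statement, made before unblinding, of which of the two is primary.
3. A table of item #19 failures and blanks by arm and time, saying whether a blank counts as a failure.
4. A rule that a conclusion differing between the two analyses is described as not robust.

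**Cost.** A few sentences and one further model run on data already collected; no new participants, items or website changes. The drawback is that the unfiltered estimate is diluted if failed batteries carry no signal: an assumed 0.30 SD effect reads 0.285 SD at 5% failure in both arms and 0.255 SD at 15%. This is why both analyses should be shown.
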